1.1. Objectives, Endpoints, and Estimands

This table describes the objectives and endpoints related to Study EZCB.

Objectives	Endpoints
Primary	
To evaluate if LY3561774 is superior to placebo for the treatment of mixed dyslipidemia in adults.	Percent change from baseline at Day 180 for ApoB.
Secondary	
To compare the clinical response of LY3561774 to placebo.	Percent change from baseline at Day 180 for • ANGPTL3 • LDL-C • HDL-C • non-HDL-C, and • TG.
	Percent change from baseline at Day 270 for • ANGPTL3 • Non-HDL-C • LDL-C • HDL-C • ApoB, and • TG.

To characterize the pharmacokinetics of LY3561774.	Plasma concentrations of LY3561774.
To compare the effect of LY3561774 to placebo on safety endpoints.	Frequency of treatment-emergent adverse events.
To describe the safety of LY3561774 in participants with mixed dyslipidemia.	Summary of safety data, including number and incidence of TEAEs, SAEs, and discontinuations due to AEs.
Exploratory	
To assess the relationship between LY3561774 dose and clinical endpoints, and potential participant factors that may influence these relationships.	Dose-response analyses for key efficacy and safety parameters.
To assess the relationship between LY3561774 exposure and clinical endpoints, and potential participant factors that may influence these relationships.	Exposure-response analyses for key efficacy and safety parameters.
Evaluation of immunogenicity.	Incidence of treatment-emergent ADA.
To compare the effect of LY3561774 to placebo on clinical endpoints or biomarkers.	Percent change from baseline at Day 180 for • hsCRP • ApoA-I • ApoC-III • VLDL-C • UACR

	HbA1c, andFG.
To compare the effect of LY3561774 to placebo for key efficacy parameters.	Absolute change from baseline at Day 180 for Non-HDL-C LDL-C HDL-C ApoB, and TG.
	Percent change from baseline in time-averaged parameters over Days 30 to 180 and Days 120 to 270 for • ApoB • LDL-C • HDL-C • Non-HDL-C • TG.
To compare the effect of LY3561774 to placebo on hepatic fat fraction.	Percent and absolute change from baseline for MRI hepatic fat fraction at Day 180.

Abbreviations: ADA = anti-drug antibodies; AE = adverse event; ANGPTL3 = angiopoietin-like protein 3; Apo = apolipoprotein; ApoA-I = apolipoprotein A-I; ApoB = apolipoprotein B; ApoC-III = apolipoprotein C-III; FG = fasting glucose; HbA1c = hemoglobin A1c; HDL-C = high-density lipoprotein-cholesterol; hsCRP = high-sensitivity C-reactive protein; LDL-C = low-density lipoprotein-cholesterol; MRI = magnetic resonance imaging; SAE = serious adverse event; TEAE = treatment-emergent adverse event; TG = triglycerides; UACR = urinary albumin/creatinine ratio; VLDL-C = very-low-density lipoprotein-cholesterol.

Primary estimand

The primary clinical question of interest is: what is the treatment difference in the apolipoprotein B (ApoB) percent change from baseline after 180 days of treatment in participants who meet the inclusion criteria and who would have completed the Study EZCB treatment period?

The "efficacy estimand" is described by

- population: participants who meet the inclusion criteria; further details can be found in Sections 5 and 9 of the Study EZCB protocol
- endpoint: percent change from baseline in ApoB at Day 180, and
- treatment condition: the randomized treatment, without any excluded medications or additional lipid-lowering drugs.

The intercurrent events for Study EZCB are permanent discontinuation of intervention, initiation of excluded medications taken during the study, and new initiation of any lipid-lowering drug required to be on a stable regimen prior to treatment per the protocol inclusion criteria. These are handled by a hypothetical strategy wherein the potential outcome of interest is the participant's response in the efficacy measurement, if participants had adhered to the randomized treatment.

The potential outcomes related to the efficacy estimand are summarized at the population level using the difference in mean percent changes in ApoB at Day 180 between each dose of LY3561774 and placebo.

The rationale for this estimand is to study the efficacy of LY3561774 under the ideal condition that all participants adhere to the randomized treatment.

Estimand(s) for secondary objectives

The same estimand for the primary objective will be used for the efficacy endpoints for the secondary objective of comparing the clinical response of each dose of LY3561774 to placebo.

Secondary estimand: treatment-regimen estimand

The clinical question of interest is: what is the treatment difference in key lipid parameters after 180 days of treatment in participants who meet the inclusion criteria regardless of treatment discontinuation?

The treatment-regimen estimand is described by the attributes

- population: participants who were randomized and had at least one dose of study medication; further details can be found in Sections 5 and 9 of the Study EZCB protocol
- endpoint: percent change from baseline in key lipid parameters (low-density lipoprotein-cholesterol [LDL-C], non-high-density lipoprotein-cholesterol [non-HDL-C], high-density lipoprotein-cholesterol [HDL-C], triglycerides [TG], and ApoB) at Day 180, and
- treatment condition: the randomized treatment, regardless of treatment discontinuation.

The intercurrent events are handled by the treatment policy strategy where the potential outcome of interest is the response in the efficacy measurement regardless of treatment adherence.

The potential outcomes related to the treatment-regimen estimand are summarized at the population level using the difference in mean percent changes in key lipid parameters at Day 180 between each dose of LY3561774 and placebo.

The rationale for this estimand is to facilitate analysis based on the real-world scenario (that is, the intention-to-treat principle) for key lipid parameters (LDL-C, non-HDL-C, HDL-C, TG, and ApoB).

Unless otherwise specified, safety assessments will be guided by an estimand comparing the safety of LY3561774 doses with placebo irrespective of adherence to study intervention, including data collected during the treatment period and safety follow-up (that is, the treatment-regimen estimand).

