Abbreviations: AE = adverse event; ANGPTL3 = angiopoietin-like protein 3; Apo = apolipoprotein; FG = fasting glucose; HbA1c = hemoglobin A1c; HDL-C = high-density lipoprotein-cholesterol; hsCRP = high-sensitivity C-reactive protein; LDL-C = low-density lipoprotein-cholesterol; MRI = magnetic resonance imaging; SAE = serious adverse event; TEAE = treatment emergent adverse event; UACR = urinary albumin/creatinine ratio; and VLDL-C = very-low-density lipoprotein-cholesterol.

Primary estimand

The primary clinical question of interest is

What is the treatment difference in ApoB percent change from baseline after 180 days of treatment in participants who meet the inclusion criteria and would have completed the treatment period?

Efficacy estimand attributes

This table describes the efficacy estimand attributes.

Efficacy Estimand Attribute	Description
Population	Participants who meet the inclusion criteria. Further details can be found in Sections 5 and 9.
Endpoint	Percent change from baseline in ApoB at Day 180.
Treatment condition	The randomized treatment.
Population-level summary	Difference in mean percent changes in ApoB at Day 180 between LY3561774 and placebo.

Intercurrent events

The intercurrent events including the following are handled by the hypothetical strategy:

- Permanent discontinuation of intervention.
- Initiation of excluded medications taken during the study.
- New initiation of any lipid-lowering drug required to be on a stable regimen prior to treatment per the protocol inclusion criteria.

The potential outcome of interest is the response in the efficacy measurement if participants adhere to the randomized treatment.

Rationale for the efficacy estimand

This Phase 2 study aims to study the efficacy of LY3561774 under the ideal condition that all participants adhere to the randomized treatment.

Estimand(s) for secondary objectives

The same estimand for the primary objective will be used for the secondary clinical response endpoints.

Unless specified otherwise, safety assessments will be guided by an estimand comparing safety of LY3561774 doses with placebo irrespective of adherence to study intervention, including data collected during the treatment period and safety follow-up.

4. Study Design

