5.1. Inclusion Criteria

Participants are eligible to be included in the study only if all of the following criteria apply:

Age

1. Must be 18 years of age or older at the time of signing the informed consent.

Type of participant and disease characteristics

2. Have fasting TGs within the range of 150 to 499 mg/dL (1.69 to 5.64 mmol/L) at screening.
3. Have fasting LDL-C \geq 70 mg/dL (1.81 mmol/L) at screening.
51. Have fasting non-HDL-C \geq 130 mg/dL (3.36 mmol/L) at screening.
4. Must be on a stable moderate or high-intensity dose of a statin (See Section 10.7.1) for at least 2 months before screening and remain on the same medication and dose for the duration of the study.

Weight

5. Have a body mass index within the range of 18.5 to 40.0 kg/m², inclusive.

Sex and contraceptive/barrier requirements

6. Are WOCBP who agree to use contraception as outlined in Section 10.4 or
Are WNOCBP as defined in Section 10.4 or
Are men who agree to use contraception as outlined in Section 10.4.

Contraceptive use by participants should be consistent with local regulations regarding the methods of contraception for those participating in clinical studies.

Definitions and contraception requirements for participants in this study are provided in Section 10.4.

Informed consent

7. Are capable of giving signed informed consent as described in Section 10.1.3, which includes compliance with the requirements and restrictions listed in the ICF and in this protocol.

Other inclusions

8. Have not started a structured weight loss program within 3 months of screening, or plan on starting a program during the study.
9. If taking hypertensive therapy, doses must be stable 30 days prior to screening.
10. Are reliable and willing to make themselves available for the duration of the study and are willing to follow study procedures.
11. Have an optimal MRI image quality at screening, as assessed by central laboratory.

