- 26. Have active severe liver diseases, such as cirrhosis, active hepatitis, or biliary obstruction with hyperbilirubinemia.
- 27. Have a history of infection within 14 days before screening that, in the opinion of the investigator, would potentially affect participant safety within the study or interfere with the interpretation of data.
- 28. Have HIV infection or are positive for HIV antibodies.
- 29. Have current infection with hepatitis B virus or positive for hepatitis B surface antigen.
- 30. Have a current infection with hepatitis C virus or positive hepatitis C virus antibody.

Diagnostic assessments

- 31. Have clinically relevant anemia, as defined by the investigator.
- 32. Have laboratory values, in relation to the reference range,
 - ALT >3.0X ULN or
 - ALP >1.5X ULN or
 - TBL >1.5X ULN, except for participants diagnosed with Gilbert's syndrome.
- 33. Have an eGFR <30 mL/min/1.73 m².
- 34. Have a pulse rate >100 bpm, a repeat measure is allowed.
- 35. Have uncontrolled hypertension with a resting blood pressure ≥180 mm Hg systolic and/or ≥100 mm Hg diastolic, a repeat measure is allowed.

Prior/concomitant therapy

- 36. Have used or are taking products for the purpose of lowering lipid levels. This includes lipid-regulating medication, over-the-counter products, or herbal therapies.
See Section 10.7.3 for details on prohibited treatments and the timeframe relative to screening.
Exceptions: Statins, PCSK9 inhibitors, bempedoic acid, and ezetimibe.
- 37. Have within 3 months of screening, initiated treatment with SERMs, estrogens, progestins, testosterone, or thyroid hormone therapy.
- 38. Have or are currently taking HIV protease inhibitors, cyclophosphamide, or systemic retinoids.
- 39. Have within 6 months of screening had treatment with any oligonucleotide, including small interfering ribonucleic acid.
Exception: mRNA vaccines.
- 40. Have within 3 months of screening treatment with systemic corticosteroids, cyclosporine, isotretinoin, or anabolic agents.
Exceptions: local, topical, intra-articular, inhalation, or nasal corticosteroids.
- 41. Have within 1 month prior to screening treatment with
 - a. warfarin or other coumarins
 - b. direct thrombin inhibitors
 - c. Factor Xa inhibitors, or

- d. Heparins or heparinoids.
42. Are currently using a medication associated with weight gain or weight loss.

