2.1. Multiplicity Adjustment

All treatment comparisons will be performed at the full significance level of 0.05. No adjustment for multiplicity will be performed.

3. Analysis Sets

This table defines the analysis population and datasets for the purposes of analysis.

Population	Description
Screened	All participants who signed informed consent.
Randomized	All participants who are randomly assigned to a treatment arm.
EAS	Data obtained during the treatment period from all randomly assigned participants who are exposed to at least 1 dose of the study intervention and are not discontinued due to inadvertent enrollment. Excludes data after any of
	 permanent discontinuation of intervention initiation of excluded medications taken during the study, and new initiation of any lipid-lowering drug required to be on a stable regimen prior to treatment per the protocol inclusion criteria.
	Participants will be included in the treatment group to which they were randomly assigned.
FAS	Data obtained during the treatment period from all randomly assigned participants who are exposed to at least 1 dose of study intervention, regardless of adherence to intervention, and are not discontinued due to inadvertent enrollment. Participants will be included in the treatment group to which they were randomly assigned.
SAS	Data obtained during the treatment period plus safety follow-up from all randomly assigned participants who are exposed to at least 1 dose of the study intervention, regardless of adherence to the intervention, and are not discontinued due to inadvertent enrollment. Participants will be included in the treatment group to which they were randomly assigned.

Abbreviations: EAS = efficacy analysis set; FAS = full analysis set; SAS = safety analysis set.

4. Statistical Analyses

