4.3. Primary Endpoint Analysis

The primary efficacy assessment, guided by the efficacy estimand, will be conducted using the efficacy analysis set (EAS) for the primary endpoint (percent change from baseline at Day 180 for ApoB).

The hypothetical strategy defined relative to the efficacy estimand – had participants adhered to the randomized treatment – will be used to handle the intercurrent events of permanent discontinuation of intervention, initiation of excluded medications taken during the study, and new initiation of any lipid-lowering drug required to be on a stable regimen prior to treatment per the protocol inclusion criteria. Only data collected before the occurrence of any intercurrent events will be used in the MMRM analysis. The MMRM analysis will then implicitly impute the potential efficacy measures (after the intercurrent events) if participants had not had intercurrent events.

See Section 10.7.3 of the Study EZCB protocol for a list of prohibited concomitant medications. Excluded medication and lipid lowering drugs are listed in Table EZCB.4.2.

Table EZCB.4.2 List of Medications

Prohibited Concomitant Medications and Procedures for Study EZCB			
Drug Class/Procedure	Comments		
Lipid lowering therapy including, but not limited to triglyceride-lowering medication example: Vascepa® (icosapent ethyl)	Prohibited within 4 weeks prior to screening and during the study.		
simvastatin 80 mg per dayfibratesbile acid sequestrants	Prohibited within 6 weeks prior to screening and during the study.		
over-the-counter and health food preparations o examples: red yeast rice, fish oil, omega-3 fatty acid >100 mg/day niacin >250 to <1000 mg/day or other nicotinic acid derivatives probucol	Prohibited within 8 weeks prior to screening and during the study.		
• niacin >1000 mg per day	Prohibited within 16 weeks prior to screening and during the study.		
inclisiran or any other small interfering ribonucleic acid	Prohibited within 12 months prior to screening and during the study.		
Warfarin or other coumarins	Prohibited within 1 month prior to screening and during the study.		
Direct thrombin inhibitors	Prohibited within 1 month prior to screening and during the study.		
Factor Xa inhibitors	Prohibited within 1 month prior to screening and during the study.		
Heparins or heparinoids	Prohibited within 1 month prior to screening and during the study.		

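### The SAP's efficacy estimand rules out additional lipid-lowering drugs, but its intercurrent-event list, read literally, keeps ApoB values after a new start of a permitted add-on

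*SAP*

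**What the plan says.** **The stated condition.** SAP 1.1 gives the efficacy estimand's "treatment condition: the randomized treatment, without any excluded medications or additional lipid-lowering drugs".

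**The events that implement it.** The next paragraph of SAP 1.1 begins: "The intercurrent events for Study EZCB are permanent discontinuation of intervention, initiation of excluded medications taken during the study". The third event follows, and SAP 3 repeats it in the efficacy analysis set (EAS) as "new initiation of any lipid-lowering drug required to be on a stable regimen prior to treatment per the protocol inclusion criteria". SAP 4.3 carries the same list and adds: "Only data collected before the occurrence of any intercurrent events will be used in the MMRM analysis". SAP 4.9 repeats the list when it records the change to the EAS. Protocol Section 3 has the same third event ("New initiation of any lipid-lowering drug required to be on a stable regimen prior to treatment per the protocol inclusion criteria"), but gives its treatment condition only as the randomized treatment.

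**Which drugs are involved.**
- Inclusion criterion 4 (Protocol 5.1): "Must be on a stable moderate or high-intensity dose of a statin". No other inclusion criterion requires a stable lipid-lowering drug.
- Exclusion criterion 36 (Protocol 5.2): "Exceptions: Statins, PCSK9 inhibitors, bempedoic acid, and ezetimibe". Protocol 10.7.2 lists the same four classes as permitted.
- SAP 4.3: "Excluded medication and lipid lowering drugs are listed in Table EZCB.4.2". That table reproduces the prohibited list in Protocol 10.7.3. It does not name ezetimibe, bempedoic acid or PCSK9 inhibitors as a class. It does name inclisiran and other siRNA, so those are already covered as excluded medications.

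**The concern.** The treatment condition and the event list should describe the same hypothetical world. Here the condition rules out any added lipid-lowering drug, while the list removes data only after a narrower set of starts. The primary endpoint, ApoB, is itself a lipid marker, and the protocol classes the three add-ons as lipid-regulating medication. Keeping values measured on an added drug means that the primary MMRM uses data that the stated condition excludes.

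At stake is a reproducible rule for the primary dataset. Two careful programmers could treat the same participant differently. The same estimand and EAS serve the secondary lipid endpoints (SAP 4.4.1), so the ambiguity carries over to them.

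**Working it through.** **1. Does a new start of a permitted add-on meet any listed event?**

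| Listed event | New ezetimibe, PCSK9 inhibitor (not siRNA) or bempedoic acid after randomization |
|---|---|
| Permanent discontinuation of intervention | Not in itself |
| Initiation of an excluded medication | Not named in Table EZCB.4.2; on the permitted list in Protocol 10.7.2 |
| New initiation of a lipid drug that the inclusion criteria require to be stable | No; criterion 4 names only a statin |

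No event is met, so SAP 4.3 keeps the later values. The third event read this way is also almost empty: every eligible participant is already on a statin, so at most a switch of statin could count. That suggests a wider intention that the words do not express.

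**2. The plan's own figure.** Inputs from Protocol 9.5 and SAP 5: 175 participants in a 2:1:2:2 ratio, 20% dropout (Protocol 9.5), SD 15, difference -30, two-sided alpha 0.05.
- Completers: 175 × 2/7 × 0.8 = 40, and 175 × 1/7 × 0.8 = 20.
- Standard error, 40 v 40: 15 × √(2/40) = 3.35 points. For 20 v 40: 15 × √(1/20 + 1/40) = 4.11 points.
- Noncentral-t power exceeds 0.999999 for both comparisons. The stated figure of more than 99% is reproduced.

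**3. Size of the effect.** The documents give no frequency of add-on starts and no add-on effect. I assume extra proportional ApoB lowering *e* of 10% to 40%, fully present at Day 180. SAP 4.1 analyses percent change on the log scale, so with a planned ratio of 0.70 and starter fractions p(active) and p(placebo):

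difference = exp[ln 0.70 + (p(active) − p(placebo)) × ln(1 − e)] − 1

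| Scenario | e = 10% | e = 40% |
|---|---|---|
| Equal use in both arms | -30.0% | -30.0% |
| One net starter of 40, placebo | -29.8% | -29.1% |
| One net starter of 40, 400 or 800 mg | -30.2% | -30.9% |
| One net starter of 20, 100 mg | -30.4% | -31.8% |

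For example, one placebo starter at 40%: exp(ln 0.70 − 0.025 × ln 0.60) − 1 = -29.1%. On the raw scale one placebo starter moves the difference by 10/40 = 0.25 to 40/40 = 1.0 points, which is 0.07 to 0.30 of the 3.35-point standard error.

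**4. A deliberately unfavourable illustration.** Six of 40 start on placebo and none on active, each with 40% extra lowering.
- Log scale: exp(ln 0.70 − 0.15 × ln 0.60) − 1 = -24.4%.
- Raw scale: -30 + 0.15 × 40 = -24.0.
- Placebo SD: √(15² + 0.15 × 0.85 × 40²) = 20.7.
- Welch power at -24.0: 0.99995 (40 v 40) and 0.9989 (20 v 40).

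This scenario is arbitrary. Nothing in the documents caps the number of starters at six, so it is not an upper bound.

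**The case against.** **The table may already settle it.** SAP 4.3 points to Table EZCB.4.2 for both excluded medications and lipid-lowering drugs, and the table's lipid entry is open-ended. This can be taken two ways.
- If the open-ended entry covers every lipid-lowering therapy, a new add-on is an excluded medication and is flagged. But that places drugs on the protocol's permitted list inside its prohibited table.
- If the table instead defines which additional drugs the condition means, an add-on not named there lies outside the condition by design, and nothing conflicts. But the table is the prohibited list, so the second half of the condition would then add nothing to its first half.

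Both readings are arguable. They give opposite rules for the same participant, which supports settling the wording.

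**Background therapy should be stable.** Protocol 6.8 asks for stable dosages and for consultation before any new medicine. This makes new starts less likely. It is not an inclusion criterion, however, so it does not trigger the third event, and it does not prohibit a new start. The exemption and the permitted list do not say whether they extend to one.

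**The EAS already matches the list.** It does, and the alignment described in SAP 4.9 was achieved in that sense. The mismatch lies one step earlier, between the condition and the list in SAP 1.1.

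**The effect is small.** This stands. After randomization, sites receive no lipid-panel results and ApoB only at Day 270 (Protocol 10.2), which limits lipid-driven starts.

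**Conclusion.** Wrong as written, but minor. Followed literally, the SAP's data-exclusion rule departs from its own stated treatment condition for new starts of three permitted drug classes.

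Under the assumed 10% to 40% extra lowering, one net starter of 40 shifts the estimate by less than 1 point, and one of 20 on 100 mg by up to 1.8 points. The direction depends on which arm has more starters; equal proportional use leaves -30.0% unchanged.

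A reader might infer more than the documents support:
- *That the superiority conclusion is threatened.* Even in the six-of-40 illustration, power is about 99.9%.
- *That the primary estimate is known to be biased one way.* No frequencies or add-on effects are given.
- *That the protocol contradicts itself in the same way.* Its Section 3 treatment condition does not mention additional lipid-lowering drugs, so the explicit conflict is in the SAP only.

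**What to change.** Change the SAP only, before unblinding. In SAP 1.1, 3, 4.3 and 4.9, reword the third event as: *new initiation after randomization of any lipid-lowering drug, including those permitted as background therapy*. Exclude later values from the EAS. Record the change in SAP 4.9 as a departure from the event list in Protocol Section 3. Protocol 9.3.1 asks for an amendment only if a principal feature changes, and SAP 4.9 already records one departure for the EAS.

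Narrowing the treatment condition in SAP 1.1 would also remove the conflict. Widening the event is preferable because it keeps the stated hypothetical question. The removed values still contribute to the treatment-regimen analysis of ApoB percent change at Day 180 on the full analysis set (SAP 1.1, 4.5.2).

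Cost: one wording change in four SAP sections and one programmed flag. Medication names and start and end dates are already collected (Protocol 6.8). The downside is slightly fewer EAS observations, with values after the event left to the MMRM's implicit imputation. The change concerns an analysis rule and takes no position on which drugs are permitted.
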